Patients at high risk of emergency hospital admission (top quintile) or with long-term conditions are offered enrolment in the programme during the course of a consultation with their General Practitioner (GP). Enrolment on the programme is considered complete if patients consent to be enrolled on the programme and consent for their data to be shared with the WELC Integrated Care Programme partners, and this consent is recorded on the electronic patient record by the GP. Enrolment started in April 2012, with a total of 29 patients enrolling in the first 12 months. The following fiscal year (2013-2014) saw another 906 patients enrol on to the programme. Numbers are increasing rapidly, with currently 11,940 patients on the pathway (1.3% of all patients, in comparison to the 20% targeted) (source: WELC Data Cube).

The integrated care programme is trying to achieve its goals through a combination of patient engagement; joint decision making and accountability; clinical leadership and culture development; information sharing and decision support; and aligned incentives and reimbursement models. Although patients are either enrolled or not enrolled on the programme, the actual intervention may differ from patient to patient and across different CCGs. The Integrated Care Programme comprises nine categories of interventions:

1. Self-care, behaviour and expectation management;
2. Care planning;
3. Health and social care navigation;
4. Case management;
5. Specialist input in the community;
6. Discharge support for mental health patients from secondary to primary care;
7. Rapid response with short term re-ablement;
8. Mental health liaison; and
9. Discharge support from the acute community.

The exact interventions can be specific to local arrangements, and so are difficult to generalise across a larger population. Therefore, the evaluation proposed in this protocol aims to evaluate the overall effect of enrolment onto the integrated care pathway, rather than looking at effect of the individual

interventions offered during this pathway. We will, however, try to describe the occurrence of particular interventions.

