A small number of patients provided consent to be on the pathway or for their data to be shared but not both. Because there is some ambiguity about the care received by these patients, they will be excluded from the study.

The initial findings of the evaluation will be based on outcomes over the six months following enrolment. This relatively short follow-up period will allow for timely results by the end of 2015. Further analysis will be based on a follow-up period of twelve months following enrolment; however patient-level data required for this analysis are not expected to be available before February 2015 (see ‘Timescale’ below for more details).

Intervention

The focus of this study is to evaluate the overall integrated care pathway, and thus we will assess patient outcomes from the date of enrolment onto this pathway. After the enrolment on the programme a patient will receive specific interventions at varying intervals that greatly influence the effect of the overall ‘treatment’ (see figure below).

We will report the overall duration of time spent on the integrated care pathway using Kaplan-Meier curves (Kaplan & Meier 1958). These show the proportion of patients remaining on the pathway after various numbers of days spent on the pathway. In some cases, the lag between enrolment on the pathway and receiving first ‘different-from-normal’ care might be substantial, and so we will explore whether the individual interventions illustrated in the figure below can be identified from the line-level data.

Endpoints

The Integrated Care Program has identified a wide range of Key Performance Indicators (KPIs). These indicators span: quantitative metrics to assess how care is being integrated; metrics on reviews of individual patient cases and care plans; and metrics of health care utilisation. This last category of indicators is most relevant to this study and includes:

- Number of GP appointments (*e.g.*, per head, per 12 months);
- Number of urgent referrals;
- Number of hospital bed days per patient;
- Number of weekend discharges from hospital;
- Secondary care cost (PbR);
- Number of emergency hospital admissions;
- Number of avoidable hospital admissions;
- Number of A&E attendances; and
- 30-day hospital readmission rates.

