Our primary endpoint is the number of emergency hospital admissions per patient, which is a commonly used endpoint in evaluative studies of integrated care. Our secondary endpoint is the number of hospital bed days per patient over twelve months, as this reflects changes to the length of stay in hospital as well as the number of admissions.

Other endpoints will be the notional cost of care per patient, including primary and secondary care cost and other indicators listed above.

Sample size calculation

Our sample size will be sufficient to identify a 15% change in emergency admissions between the enrolled patients and the matched control group. Our sample size calculation was performed in SAS with 90% power and a two-sided p-value of 0.05. We assumed an average number of emergency admissions per patient per year of 0.6 with a standard deviation of 1.4. These assumptions are based on a previous study with a similar population base (Steventon, Bardsley, Billings, Dixon, et al. 2012).

The sample size calculation indicate that in order to identify a 15% change in emergency admission a sample size of 10,174 is required in case of a balanced sample (1 control per enrolled patient), or 11,445 in case of a sample with two controls per enrolled patient. In comparison, we estimate that our study will include at least 6,360 integrated care patients. In a matched control design with one control patient per integrated care patient, the total sample size would therefore be 12,720 patients. If there were two control patients per integrated care patient, the total sample size would be higher, at 19,080.

Control group

In the absence of a randomised controlled trial, we will compare the outcomes of the integrated care cohort with a retrospectively matched control group. In other words, line-level routine, patient information will be used to characterise the integrated care patients as well as possible, and then select, for every patient, matched controls that were not enrolled onto the programme but had similar observed characteristics to the enrolled patient. These matched patients will form the control group for the evaluation of the programme.

Control patients will be registered with a general practice in the WELC area, and will not have been enrolled onto the integrated care pathway at any point before the end of our follow-up period.

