Preliminary analysis of aggregated data from the WELC Integrated Care Programme (using the Data Cube) suggests that the pool of potential matches is sufficiently large to select matched controls within cluster (*i.e.*, geographically clustered GPs) and within the same risk-band (top 0.5%, 0.5-5%, or 5-20%). This is because enrolment rates at cluster level vary between 17% and 38%, and enrolment rates for the different risk-bands are 50%, 24% and 2%, respectively.

Matching will be done to optimise the similarity of integrated care and matched control groups with respect to variables that are likely to be predictive of the endpoints. These variables will include:

predictive risk score; age; gender; ethnicity; prior primary and secondary care utilisation; a measure of socioeconomic deprivation (the Index of Multiple Deprivation, attributed to the Lower Super Output Area of residence); existing diagnoses of health care conditions; and numbers of prescription medications. Many of these variables feature in the Combined Predictive Model (Wennberg et al. 2006), but are included in our matching algorithm so that the groups will be similar in terms of these more detailed variables as well as the overall risk score.

To increase the number of potential controls available for the analysis, we will assign each potential control up to 12 index dates, one for each month from January 2014 to December 2014, assuming that the patient is alive at each of these time points. Baseline variables (*e.g.*, age and prior primary and secondary care utilisation) will then be calculated at each of these index dates, and each control patient will provide the matching algorithm with up to twelve observations.

Matched control observations will be selected using the genetic matching algorithm, which is a computer-intensive search procedure that produces more closely balanced groups than traditional approaches such as nearest neighbour matching on the propensity score (Sekhon & Grieve 2012). Balance will be assessed using the standardised difference, which is defined as the difference in means as a proportion of the pooled standard deviation (Austin 2009). Although the standardised difference would ideally be minimised without limit, a threshold of 10% has been used to describe meaningful difference (Normand et al. 2001). We will adjust the parameters in the genetic matching algorithm until we obtain standardised differences below these thresholds.

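### A control observation can start during a hospital stay, while enrolled follow-up starts through a GP consultation, so control bed days can include the end of stays already in progress

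*Protocol*

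**What the plan says.** **Controls.** Under Methods, Control group, a potential control receives "up to 12 index dates, one for each month from January 2014 to December 2014, assuming that the patient is alive at each" date. The same section requires registration with a practice in the area and that the control "will not have been enrolled onto the integrated care pathway at any point before the end of our follow-up period". No condition concerns being in hospital on the date.

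**Enrolled patients.** The Introduction says that eligible patients "are offered enrolment in the programme during the course of a consultation with their General Practitioner (GP"), and that enrolment is complete once both consents are given and "this consent is recorded on the electronic patient record by the GP". Methods, Intervention then fixes the start of outcome counting: "we will assess patient outcomes from the date of enrolment onto this pathway".

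**Endpoint.** Methods, Endpoints: "Our secondary endpoint is the number of hospital bed days per patient over twelve months". There is no rule for a stay that began before the index date and ended after it. Methods, Study cohort adds that the first results will use six months of follow-up.

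**Safeguards.** The matching variables listed under Control group include the risk score, demographics, deprivation, diagnoses, prescriptions and earlier primary and secondary care use. Inpatient status on the index date is not listed. The regression under Statistical method adjusts for what imbalance remains in the baseline variables.

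**The concern.** Time zero is set by different processes in the two groups, and they differ on something tied directly to bed days. A monthly calendar date can fall anywhere, including inside a hospital stay. A consultation with a GP rarely does.

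The stays that a fixed date catches are not typical: a long stay covers more dates, so it is more likely to be caught, and its expected remaining length can exceed the mean of all stays. Matching on earlier hospital use need not exclude such a record, because the admission now in progress is itself earlier use and can make the person look like a good match. A stay of more than a month can also enter at more than one index date, since one person may supply up to twelve observations and matching is with replacement.

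Bed days is the one endpoint that the protocol names as secondary. If the tails are counted, this component shows a saving even when the pathway has no effect, and a larger sample does not reduce it.

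**Working it through.** **The plan's own figures first.** Methods, Sample size calculation gives 0.6 emergency admissions per patient-year, SD 1.4, a 15% change (0.6 × 0.15 = 0.09), 90% power and two-sided 0.05.

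- One control each: n per group = 2 × 1.4² × (1.960 + 1.282)² / 0.09², which gives 5,086, or 10,172 in total (stated 10,174).
- Two controls each: 3,814 enrolled and 7,628 controls, 11,442 in total (stated 11,445).

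The stated totals agree with the t-test version of the same calculation. They concern admissions and are not in question here.

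**Inputs for the tail.** The admission rate of 0.6 a year is the protocol's. Mean stay L and its coefficient of variation CV are not in the documents, so they are assumptions.

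**Formulas,** for a date that falls at random:

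- Share of control dates inside a stay: 0.6 × L / 365.
- Mean remaining stay for those caught: L(1 + CV²) / 2.
- Tail per control: the product of these two.
- Tail as a share of a year's bed days (0.6 × L): L(1 + CV²) / 730. The admission rate cancels.
- Over six months the tail is nearly the same but the bed days halve, so the share is about L(1 + CV²) / 365.

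| L (days) | CV | Dates inside a stay | Tail per control (days) | Share, 12 months | Share, 6 months |
|---|---|---|---|---|---|
| 5 | 1.5 | 0.8% | 0.07 | 2.2% | 4.5% |
| 8 | 1.5 | 1.3% | 0.17 | 3.6% | 7.1% |
| 8 | 2 | 1.3% | 0.26 | 5.5% | 11.0% |
| 12 | 1.5 | 2.0% | 0.38 | 5.3% | 10.7% |

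For the second row: 8 × (1 + 2.25) = 26; 26/730 = 3.6% and 26/365 = 7.1%. Pairing the longest mean with the widest spread (L = 12, CV = 2) gives 60/730 = 8.2%.

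**Does matching on earlier admissions remove it?** This was simulated with no true effect: admissions with mean 0.6 and SD 1.4, lognormal stays, a constant admission rate for each person while out of hospital, enrolled patients out of hospital at time zero, controls on a random date, and exact matching on the prior-year admission count.

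- L = 8, CV = 1.5: 4.20 bed days enrolled against 4.35 control, an apparent change of −3.4%. Among people with at least one prior-year admission: 12.19 against 12.76, or −4.5%.
- Across L = 6 to 12 and CV = 1 to 2: −1.6% to −7.3% overall, and −2.1% to −9.2% among those with a prior admission.
- Number of admissions: a difference of 0.0% to 0.3%.
- Bed days from new stays only: a difference of 0.0% to 0.4%.

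**The case against.** The strongest objection is that the harm depends on a counting rule that the protocol never states. A reader might infer that control bed days do include these tails. The text does not say so. Its reason for choosing the endpoint, that it captures length of stay as well as admissions, would also suit a count limited to stays that begin in follow-up, and under that count the artefact vanishes. Such a rule may stand in an analysis plan not available here. This part stands: the inclusion is conditional. The control index-date rule, however, is fixed in the protocol itself and stays asymmetric whatever that plan says.

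Four further inferences go beyond the documents:

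- *That no enrolled patient could be an inpatient at time zero.* The Introduction describes a consultation and a GP's record entry. It does not say that the recorded date is the consultation date, nor does it exclude inpatients. Few is supported; none is not.
- *That the planned matching cannot help.* Only the prior-year admission count was tested. The planned set is wider, and the form of its hospital-use variables is open; recent bed days or short look-back windows might remove part of the tail.
- *That the overall bias must favour the pathway.* The direction is established for this component only. Discharge support is among the interventions, so enrolment may tend to follow a recent discharge, and that could change the net result.
- *That the cost endpoint carries the same bias.* The protocol does not say that cost is built from bed days.

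The size is also modest. With 6,360 enrolled and independent controls, the four scenarios put the tail at 0.41 to 0.99 standard errors with one control each, or 0.48 to 1.15 with two. The bed-day difference detectable with 90% power is about 15% to 20%. That limits how often this component alone would change a conclusion, but not the shift in the estimate.

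**Conclusion.** The concern holds in a conditional form. The asymmetry in time zero is in the text, and neither the listed matching variables nor the regression adjustment names inpatient status on the index date. On the plain reading of the endpoint, with all days from the index date counted, this component alone makes control bed days about 2% to 6% too high over twelve months in the four scenarios, and roughly twice that in the six-month results that are to come first.

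These sizes rest on assumed lengths of stay, on enrolled patients being out of hospital at time zero, and on no help from matching variables beyond the prior admission count. Only emergency stays are counted. The primary endpoint is essentially unaffected, and the stated sample sizes stand. It is a modest, avoidable bias in the named secondary endpoint, and worth removing because the remedy is simple.

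**What to change.** One of two changes is enough:

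1. In Methods, Control group, make an index record ineligible if the person is an inpatient on that date (admitted before it, discharged after it), and apply the same status rule to enrolled patients at enrolment.
2. In Methods, Endpoints, define bed days in both groups as days within follow-up from stays that begin on or after the index date.

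Under the simulation's assumptions the first removes the difference by construction, and the second leaves 0.0% to 0.4%. If the first is chosen, the protocol should still say how stays in progress at time zero are counted.

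**Cost.** The first is a filter on admission and discharge dates, which the admitted patient care data requested under Data specification should carry. At 0.6 emergency admissions a year it loses 0.6 × 5/365 = 0.8% to 0.6 × 12/365 = 2.0% of control records. The loss is larger if elective stays count or among higher-risk people: 3.4% to 6.4% in the simulation for those with a prior-year admission. It also loses any enrolled patients who were inpatients at enrolment, probably few. The second loses no records, but the endpoint then leaves out the remaining days of stays already in progress, in both groups.

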We propose to evaluate the integrated care programme using a (matched) control group, rather than solely tracking metrics using the data cube for intervention patients. Looking at patient level data, and matching patients enrolled in the programme with similar patients who were not enrolled, allows us to compare the outcome measures of enrolled patients with a counterfactual. This is particularly important given the tendency of patients with a history of hospital admissions to see reductions in admissions over time even in the absence of a specific intervention ('regression to the mean') (Roland et al. 2005).

The first step of the evaluation would be to assess the feasibility of the matched control approach. There are risks that we might not find controls that are adequately matched to enrolled patients on observed baseline variables, or that there might be unobserved confounding (*e.g.*, as indicated by differential mortality rates between enrolled patients and the control group). Provided adequate controls can be found, we propose to evaluate the programme as described below.

METHODS

Study cohort

We will study patients enrolled onto the integrated care pathway in 2014 (*i.e.*, between 1 January 2014 and 31 December 2014) who were in the top 20% in terms of their risk of emergency hospital admission and who were aged fifty years or over. The cohort will include patients from all three CCGs, though we will also analyse the patients in the three CCGs separately.

This cohort has been chosen to ensure a sufficiently large study cohort of at least 6,360 patients (*i.e.*, the difference between the total number of patients enrolled on 1 January 2015 and 1 January 2014, source: WELC Data Cube). The total number of patients in the cohort is expected to be higher than this, as enrolled patients who died, or moved out of the three CCGs are not included in this total.

This cohort includes 85 per cent of patients currently enrolled in the programme. By limiting the study to this cohort ensures that sufficient information is used to evaluate the effect of the programme for different age groups robustly. Evaluation of the programme for younger patients, or patients that are less at risk of emergency hospital admission would add too much uncertainty to the study's findings at this stage. Limiting the cohort also allows for the matching to be completed in a timely manner, as matching algorithms used are very time consuming.

[figure not shown]

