We will require all data sets to be pseudonymised before transfer; no patient identifiable information (*e.g.*, name, address, full date of birth) are required to complete the analysis. Pseudonymising NHS number (*i.e.*, apply a one-way hash algorithm to the NHS number, only known to the data controller) allows the data to be updated and extended, if necessary. The data sets will need to include line-level data for the top twenty per cent of patients at risk of emergency hospital admission aged over fifty years in the WELC area¹, spanning the period 1 January 2011 to 31 December 2015. Both age and risk-score vary over time, so the exact definition of these extracts will be defined in the detailed specification. We will need Read-coded GP data on registrations with GPs, prescriptions, diagnoses, and encounters, together with line-level data from the admitted patient care, outpatient and accident and emergency commissioning data sets. It would greatly assist us if some derived variables were available for the analysis (for example, the Combined Model score and constituent variables) – this would also help us standardise our variable definitions with those used locally.

¹ Note that only data from Tower Hamlets CCG and Newham CCG is to be included.

References

- Austin, P.C., 2009. Balance diagnostics for comparing the distribution of baseline covariates between treatment groups in propensity-score matched samples. *Statistics in Medicine*, 28, pp.3083–3107.
- Kaplan, E.L. & Meier, P., 1958. Nonparametric estimation from incomplete observations. *Journal of the American Statistical Association*, 53(282), pp.457–481.
- Normand, S.-L.T. et al., 2001. Validating recommendations for coronary angiography following acute myocardial infarction in the elderly: a matched analysis using propensity scores. *Journal of Clinical Epidemiology*, 54(4), pp.387–398. Available at: <http://www.ncbi.nlm.nih.gov/pubmed/11297888>.
- Roland, M. et al., 2005. Follow up of people aged 65 and over with a history of emergency admissions: analysis of routine admission data. *BMJ*, 330, pp.289–292. Available at: <http://www.bmj.com/content/330/7486/289.short> [Accessed August 21, 2012].

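### No minimum registration before the index date is required and time registered is not a listed matching variable, so patients with an incomplete look-back can be matched on under-recorded prior use

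*Protocol*

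**What the plan says.** Under Study cohort, the enrolled group is made up of people enrolled in 2014 "who were in the top 20% in terms of their risk of emergency hospital admission and who were aged fifty years or over". No prior period on a local practice list is required.

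Under Control group, "Control patients will be registered with a general practice in the WELC area", with no duration attached. Each potential control receives up to twelve monthly index dates in 2014, "assuming that the patient is alive at each of these time points". Baseline variables follow the same timing: "age and prior primary and secondary care utilisation) will then be calculated at each of these index dates". The matching list covers risk score, demographics, deprivation, prior utilisation, diagnoses and prescriptions. Time registered is not on it.

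Under Data specification, the request is for "line-level data for the top twenty per cent of patients at risk of emergency hospital admission aged over fifty years in the WELC area", "spanning the period 1 January 2011 to 31 December 2015". Registration data are included: "We will need Read-coded GP data on registrations with GPs, prescriptions, diagnoses, and encounters". Age and risk score change over time, "so the exact definition of these extracts will be defined in the detailed specification". The section does not say whether hospital or GP activity before a patient joined a WELC practice will be in the extract.

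Moves after the index date are dealt with. Statistical method keeps people who move away in the main analysis, and Subgroup analysis adds a person-years version with an offset. Nothing equivalent covers time before the index date.

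**The concern.** The Introduction justifies a matched control group largely by regression to the mean in people with earlier admissions, so prior utilisation carries much of the design. A prior count is comparable between two people only if both were observed for the same length of time.

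Suppose someone joined a local practice six months before the index date and earlier activity is not in the extract. Two recorded admissions then mean two in six months, yet the matching treats them like two in twelve. The matched control has the same recorded history but a lower underlying rate. If such people make up a larger share of one group, the primary comparison is biased while the standardised differences on recorded variables can still pass the 10% threshold.

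Equal shares cannot be taken for granted. An enrolled patient enters once, at a date set by a GP consultation and consent, while a control may offer up to twelve observations. The section on unobserved confounding accepts that professionals may have favoured enrolling some kinds of patient.

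**Working it through.** **Inputs from the Protocol (Sample size calculation).** Mean 0.6 emergency admissions per patient-year, SD 1.4, a 15% change, 90% power, two-sided 0.05.

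**Inputs assumed here.** A 12-month look-back, matching on the prior admission count alone, months before arrival unobserved and treated as no use, and the share of arrivals. The Protocol gives none of these.

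**1. The plan's own figures.** The target difference is 0.15 × 0.6 = 0.09.

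- One control each: n = 2 × 1.4² × (1.960 + 1.282)² / 0.09² = 2 × 1.96 × 10.5074 / 0.0081, which rounds up to 5,086 per group, or 10,172 in total. The stated figure is 10,174.
- Two controls each: 1.5 × 1.96 × 10.5074 / 0.0081 gives 3,814 enrolled, or 3 × 3,814 = 11,442 in total. The stated figure is 11,445.

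Both reproduce to within a few patients, and this point does not change them.

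**2. Spread of underlying rates.** In a gamma-Poisson model the variance is μ + μ²/k. With 1.4² = 1.96, k = 0.36 / (1.96 − 0.6) = 0.265 and b = k/μ = 0.441.

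**3. Same recorded count, different observed time.** Given y admissions in a fraction t of the year, the expected rate is (k + y)/(b + t). Relative to full observation the ratio is (b + 1)/(b + t), whatever y is:

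| Months observed | t | Ratio |
|---|---|---|
| 3 | 0.25 | 1.441/0.691 = 2.09 |
| 6 | 0.50 | 1.441/0.941 = 1.53 |
| 9 | 0.75 | 1.441/1.191 = 1.21 |

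**4. Average over arrivals.** Let arrivals have the plan's true mean of 0.6. Their recorded mean is 0.6t. Fully observed controls with those same counts have an average rate of (k + 0.6t)/(b + 1). At t = 0.5 this is 0.565/1.441 = 0.392, which is 0.208 below 0.6. The expression is linear in t, so arrivals spread evenly over the year give the same 0.392.

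**5. Effect on the rate ratio.** If the enrolled group has an excess share f of such arrivals, the matched control mean is 0.6 − 0.208f:

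| f (assumed) | Control mean | Bias in rate ratio | Part of the 0.09 target |
|---|---|---|---|
| 2 points | 0.5958 | 0.7% | 5% |
| 5 points | 0.5896 | 1.8% | 12% |
| 10 points | 0.5792 | 3.6% | 23% |

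At 5 points the bias is about 0.9% if nine months are observed (control mean for arrivals 0.496) and about 2.7% if three are (0.288).

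**6. Direction.** An excess of arrivals among enrolled patients pushes the rate ratio upwards and would mask a benefit. An excess among controls does the reverse. With equal shares the bias is about nil.

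**The case against.** The strongest objection is that the mechanism depends on a fact not in the Protocol. A reader might infer that use before arrival is counted as zero. Nothing says so. The extract is for identified patients over five years, linked by a hashed NHS number, and it may include activity from before they joined. Its definition is expressly left to a later specification. This stands, and it makes the bias conditional.

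Second, look-back lengths and rules for incomplete history commonly sit in an analysis plan or data specification, and the list of matching variables is introduced in open terms. This stands for the look-back length, whose absence is not the complaint here. It has less force for who may enter and what is matched on, because the Protocol does state those rules.

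Third, a reader might infer that no planned check could reveal the problem. The mortality comparison and the simulated-confounder analysis both address enrolled patients who are sicker than their records suggest. They might signal residual imbalance. They would not identify this cause, and they may miss a bias of this size.

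Fourth, the illustration credits no other variable. Risk score, diagnoses, prescriptions and primary care use would absorb part of the difference, although some may share the same gap. Restriction to the top risk quintile would also tend to screen out people whose history looks short. This stands, and it is why the figures are an upper illustration.

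Finally, multiplying the difference in shares by the 53% excess gives a larger figure, 0.05 × 0.53 = 2.7% per five points. That assumes arrivals have the same recorded counts as everyone else, so their true mean would be well above 0.6. If arrivals have the plan's mean, their recorded counts are lower and the bias is 1.8%.

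**Conclusion.** The point holds in a limited form. The Protocol admits patients with any length of prior registration in both groups and does not list registration length as a matching variable, so matching on under-recorded prior use is possible.

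On the plan's mean and SD, a 5-point difference in the share of arrivals would move the rate ratio by about 1.8%, roughly an eighth of the 15% target. A 10-point difference would use up almost a quarter of it. These sizes rest on pre-arrival activity being absent, a 12-month look-back, matching on the admission count alone and assumed shares. The documents do not establish that any bias exists, or its direction. The change is still worth making because it costs little and the counts it produces would show whether the issue matters.

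**What to change.** 1. Add months of WELC registration before the enrolment or index date to the matching variables, the balance table and the regression adjustment, in both groups. Registration data are already requested, and the window from January 2011 gives at least 36 months before any 2014 index date. The footnote to Data specification limits the extract to two CCGs, so count months within the area that the extract covers.
2. Report for each group how many patients have an incomplete look-back, and state in the data specification whether activity before arrival is included.
3. Run a sensitivity analysis restricted to patients registered for the whole look-back used for prior utilisation (for example, 12 months).

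Step 1 excludes no one from the main analysis. The cost is one derived variable and slightly harder matching. The restricted analysis loses some precision. If the counts in step 2 are small or similar between groups, or pre-arrival activity turns out to be captured, the matter is settled.
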